#### 9.5.2.2. Other Safety

##### Vital Signs

Vital signs (temperature, pulse, blood pressure, and respiration rate) will be summarized by baseline and change from baseline to each scheduled assessment time with descriptive statistics.

##### Laboratory Tests

Laboratory test results will be summarized by baseline and change from baseline to each scheduled assessment time with descriptive statistics.

Number and percentage of patients with a treatment-emergent potentially clinically significant value (PCSV) will be summarized for each clinical laboratory test.

Shift tables based on baseline normal/abnormal and other tabular and graphical methods may be used to present the results for laboratory tests of interest.

Listings will be provided with flags indicating the out of laboratory range values.

#### 9.5.2.3. Treatment Exposure

The duration of exposure during the study will be presented and calculated as:

QW dosing: (Date of last study drug injection – date of first study drug injection) + 7 days,  
Q2W dosing: (Date of last study drug injection – date of first study drug injection) + 14 days.

The number (%) of patients exposed to study drug will be presented by specific time periods. The time periods of interest will be specified in the SAP.

In addition, duration of exposure during the study will be summarized using number of patients, means, standard deviation, minimums, medians, and maximums.

A summary of the number of doses will be provided.

#### 9.5.2.4. Treatment Compliance

The compliance with protocol-defined investigational product will be calculated as follows:

Treatment Compliance =

$$\frac{\text{(Number of investigational product injections during exposure period)}}{\text{(Number of planned investigational product injections during exposure period)}} \times 100\%$$

The treatment compliance will be presented by specific ranges. The ranges of interest will be specified in the SAP.

#### 9.5.3. Efficacy Analyses

Descriptive statistics of the efficacy endpoints will be summarized for this open-label study. These include the proportions for category endpoints and basic statistics of original, absolute, and percentage change from baseline for continuous endpoints.

All observed data will be used for analysis.

Subgroup analyses for key efficacy endpoints will be performed. The subgroup of interest and endpoints to be analyzed will be specified in the SAP.

#### 9.5.4. Analysis of Drug Concentration Data

The following analyses may be conducted:

- Sparse sampling:
  - Descriptive statistics at each sampling time
  - Mixed model analysis of variance of steady-state trough concentrations to determine between- and within-subject variability, as well as least square means

No formal statistical analysis will be performed.

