## 3. STUDY DESIGN

### 3.1. Study Description and Duration

This is a multicenter, open-label extension study to assess the long-term safety and efficacy of repeat doses of dupilumab in adults with moderate-to-severe AD who have previously participated in controlled studies of dupilumab or have been screened for a phase 3 study (R668-AD-1334 or R668-AD-1416), but could not be randomized because of randomization closure.

Enrollment will take place at approximately 500 global study sites. After providing informed consent, patients will be assessed for study eligibility at the screening visit. The screening visit in this study may coincide with the last visit in the previous study, in which case assessments that are common to both studies will be performed only once.

A loading dose of 600 mg SC (two 300 mg doses administered on the same day) dupilumab will be administered on day 1 unless the patient has received a dose of dupilumab in the 4 weeks prior to baseline. If the patient has received a dose of dupilumab in the past 4 weeks, then they will receive a single 300 mg dose at baseline. The first dose should be at least 1 week after the last dose in the previous study, and then 300 mg SC dupilumab qw starting on day 8. For patients who have not completed the study prior to the implementation of amendment 9, study drug dosing will change from dupilumab 300 mg weekly to every 2 weeks.

Patients will return for visits as specified in Section 6. In order to minimize the amount of drug that patients need to store in their home between visits, some visits will be abbreviated for the primary purpose to receive additional drug supply. The study treatment duration will be up to 5 years. The end of study visit occurs at 84 days/12 weeks after the last dose. Patients who have completed their end of treatment visit as per amendment 7 will be permitted to resume treatment with study drug. Eligible patients who have completed the end of study visit as per amendment 7 will be permitted to re-enter the study if no more than 12 weeks have elapsed since their end of

study visit. The entry criteria for patients who re-enter the study are listed in Section 4.2.3. As of the date of issue of amendment 8, this study is closed to further enrollment.

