5.6. Treatment Exposure and Observation Period

The duration of treatment exposure period during the study in week is calculated as:

$$[(\text{Date of last study drug injection} - \text{date of first study drug injection}) + 7]/7$$

regardless of unplanned intermittent discontinuations. For the exposure calculation, the two treatment gaps due to patients resuming treatment under protocol amendment 7 or 8 will be excluded. The duration of exposure will be summarized using number of patients, means, SD, minimums, medians, and maximums. A summary of the number of doses will also be provided.

The duration of observation period during the study in weeks is calculated as:

$$[(\text{Date of the last visit} - \text{date of the first study medication dose}) + 1]/7.$$

For the duration of observation period calculation, the study gap for patients who have completed the study under protocol amendment 6 then retry into the study under protocol amendment 7 will be excluded.

The duration of observation periods will be summarized using number of patients, means, SD, minimums, medians, and maximums. The number (%) of patients with observation periods will be presented by specific time periods. The time periods of interest are specified as: ≥ 1 week, ≥ 4 weeks, ≥ 12 weeks, ≥ 16 weeks, ≥ 24 weeks, ≥ 52 weeks, ≥ 76 weeks, ≥ 100 weeks, ≥ 104 weeks, ≥ 124 weeks, ≥ 148 weeks, ≥ 156 weeks, ≥ 164 weeks, ≥ 208 weeks, ≥ 260 weeks, ≥ 272 weeks.

As of protocol amendment 2, the weekly dose of dupilumab was changed from 200 mg to 300 mg. The number of patients exposed to 200 mg dose, the number of 200 mg doses and duration of treatment exposure with 200 mg and 300 mg in weeks will be calculated and summarized separately.

[Appendix 10.10](#) provides the detailed algorithm for calculating duration of treatment exposure and observational period.

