5.9. Analysis of Pharmacokinetic Data

For this study, sampling will be sparse and the types of analyses will be:

- Descriptive statistics at each sampling time

No formal statistical analysis will be performed within the scope of this plan. For the descriptive statistical analysis, concentrations below the lower limit of quantitation (LLOQ) will be set to zero.

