6.4. Analysis Visit Window

Data analyzed by-visit-analysis (including efficacy, laboratory data, visit sign, ECG) will be summarized by the study scheduled visits described in the study protocol and SAP, “Schedule of Event”. The analysis visit windows will be exhaustive so that all available values obtained from unscheduled visits, early termination (ET) visit and end of treatment (EOT)/end of study (EOS) have the potential to be summarized. No analysis visit window mapping will be applied for the PK and ADA data.

Under protocol amendment 6, the planned study duration was up to three years or until dupilumab became commercially available in the geographic region of the patient. Protocol amendment 7 was adopted in order to permit those patients in France, Germany Poland and Japan who had already completed three years of treatment to either continue or re-start treatment through 31 December 2017. Patients who were in the safety follow-up period were permitted to resume treatment. Patients who had an End of Study visit were permitted to re-enter the study after being re-consented. Patients who had completed 3 years of treatment resumed treatment in a newly created series of visits called the “treatment extension” period. All patients were scheduled to have an End of Treatment visit on or around 31 December 2017.

Protocol amendment 8 extended the treatment period for up to 5 years for patients in Poland and Finland and to September 2018 in France. Again, patients who had previously had an End of Treatment visit under Amendment 7 and were in the safety follow-up period were permitted to resume treatment. Patients who had an End of Study visit were permitted to re-enter the study after being re-consented.

As a consequence of these two amendments, certain patients from these countries experienced gaps in treatment. One gap occurred between the Amendment 6 EoT date and resumption of treatment under Amendment 7. In addition, patients from Poland experienced a second treatment gap from the EoT date under Amendment 7 and resumption of treatment under Amendment 8.

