- ^h An acceptable window for performing ophthalmology exams is within +/- 7 days of the visit date. This does not apply to the ophthalmology exam conducted at the baseline visit

Table 14: Schedule of Events – End of Treatment, End of Study, Early Termination, Unscheduled Visit, and Re-entry Visit

Study Procedures	End of Treatment	End of Study^m	Early Termination	Unscheduled Visit^l (if applicable)	Re-entry Visit^r (for patients who re-enter the study)
Visit (V)	V 44				
Week (Wk)	260	Last dose +12Wk			
Day (D) Visit Window (d)	D 1821 +/-3d	Last dose +84D +/-30d			
Treatment:					
Inclusion/Exclusion (Re-entry)					X
Informed Consent (Re-entry)					X
Demographics (Re-entry)					X
Administer study drug ^a	X				
Patient dosing diary ^b	X		X		
Study drug dispensation/account ^c	X ⁿ		X	X	
Con meds/procedures	X	X	X	X	X
Efficacy: ^d					
Patient Assessment of Pruritus Intensity via IVRS/IWRS (weekly) ^f			X ^f	X ^h	
IGA, EASI	X	X	X	X	

Study Procedures	End of Treatment	End of Study ^m	Early Termination	Unscheduled Visit ⁱ (if applicable)	Re-entry Visit ^r (for patients who re-enter the study)
	Visit (V)	V 44			
	Week (Wk)	260	Last dose +12Wk		
	Day (D) Visit Window (d)	D 1821 +/-3d	Last dose +84D +/-30d		
Safety: ^d					
Weight	X	X	X	X	
Vital signs	X	X	X	X	
Ophthalmology exam ^k (select sites and patients)		X		X ^l	
Adverse events ^e	X	X	X	X	X
Laboratory Testing: ^d					
Hematology, Chemistry	X			X	X ^o
Pregnancy test, WOCBP only ^g	Urine Monthly			X	Serum ^p
HIV screening				X	X ^q
HBsAg, HBcAb, hepatitis C antibody				X	X ^q

Study Procedures	End of Treatment	End of Study^m	Early Termination	Unscheduled Visitⁱ (if applicable)	Re-entry Visit^r (for patients who re-enter the study)
Visit (V)	V 44				
Week (Wk)	260	Last dose +12Wk			
Day (D) Visit Window (d)	D 1821 +/-3d	Last dose +84D +/-30d			
Drug Concentration and Antibody Testing: ^d					
Drug Concentration sample	X	X	X	X	
ADA sample	X	X ⁱ	X ⁱ	X	

- ^a Study drug will be administered weekly, either in the clinic or outside the clinic (self-administration or administration by a care provider).
- ^b If needed, counsel patient on proper dosing diary completion/reporting of each dose of study drug that is administered outside of the clinic.
- ^c Study drug will be dispensed to the patient for each dose that will be administered off-site between the current clinic visit and the next clinic visit. Patients will be instructed to return all study drug at each clinic visit.

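### Main-study concentration summaries pool regimens and off-drug intervals at some sampling times, so those means, and any steady-state trough estimates built on them, are not regimen-specific

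*Protocol*

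**What the plan says.** **Planned analysis.** Protocol 9.5.4 opens with "The following analyses may be conducted" and lists two items: descriptive statistics by sampling time, and "Mixed model analysis of variance of steady-state trough concentrations to determine between- and within-subject variability, as well as least square means". It names no model terms. Protocol 8.3 lists a steady-state trough among the PK variables but does not define steady state. The synopsis is firmer than 9.5.4: it commits to both the descriptive statistics and a least-square-mean analysis at steady state.

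SAP 5.9 keeps one item, "Descriptive statistics at each sampling time". It sets values below the quantitation limit to zero and adds "No formal statistical analysis will be performed within the scope of this plan". SAP 6.4 states "No analysis visit window mapping will be applied for the PK and ADA data". SAP 3.2 puts no condition on regimen or time off drug in the PK set, and SAP 1.2.4 (Table 1) says that all outputs show a single total column.

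**Dosing and follow-up.** SAP 2.3 (Table 2) records 200 mg under the original protocol and amendment 1, and 300 mg from amendment 2. Both were weekly. Under protocol 3.1, for patients still in the study at amendment 9, "study drug dosing will change from dupilumab 300 mg weekly to every 2 weeks". Follow-up was 16 weeks up to amendment 6 and 12 weeks from amendment 7. The end-of-study column in SAP 10.2 (Table 14), matched in protocol Table 7, reads "Last dose +84D +/-30d".

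**Where the plan does split.** For exposure, SAP 5.6 says "duration of treatment exposure with 200 mg and 300 mg in weeks will be calculated and summarized separately", and protocol 9.5.2.3 gives separate weekly and 2-weekly formulas. SAP 5.7 separates efficacy data around treatment gaps longer than 8 weeks. SAP 5.5 bases its 8-week limit on how far concentrations fall.

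**The concern.** A trough depends on dose, dosing interval and time since the last dose. If one row holds samples taken under different regimens, its mean moves with the mix of patients as well as with the drug's behaviour. A patient who moves from weekly to 2-weekly dosing has a planned fall in trough. A model with neither a regimen nor a visit term would count that fall as within-subject variability.

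Immunogenicity is a secondary objective, and concentrations are to be read against anti-drug antibodies (protocol 9.5.5, SAP 5.11.1). A late fall caused by the regimen change could be taken for drift or for an antibody effect. In the end-of-study row, the share of zeros depends on the last regimen and on days since the last dose, so one nominal row is hard to interpret.

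**Working it through.** The plan states no PK figure, so there is nothing to reproduce. The check asks where regimens can mix, and then how much that could matter.

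**1. Sampling times.** The current main-study schedule (protocol Tables 1 to 7) takes concentrations at baseline, weeks 48, 100 and 124, week 260 (end of treatment), end of study and early termination. None is scheduled from visit 31 to visit 43.

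- *Weeks 48 and 100.* The amendment history says these samples were added by amendment 6 (June 2016). The 200 mg dose ended with amendment 2 (June 2014). The amendment 9 summary starts 2-weekly dosing at visit 25 (week 108). These rows are essentially 300 mg weekly.
- *Week 124.* This falls after visit 25, so it can hold both intervals. Enrolment was complete by the end of May 2017 (SAP 2.2). The last patients reach week 124 at about 31 May 2017 + 124 × 7 = 868 days, or mid-October 2019. Amendment 9 is undated in the text available, so the 2-weekly share is unknown.
- *Week 260.* The global amendment 7 schedule (SAP Table 7) takes no concentration sample at its week 148 end of treatment. Mixing in this row needs some patients to have reached week 260 on weekly dosing before amendment 9. Their number is not given.
- *Early termination.* This can occur under any regimen.
- *Visits sampled before amendment 6.* Concentration samples at weeks 4, 12, 52, 60, 68 and 116 were removed by that amendment. The early ones can include 200 mg.

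**2. End of study.** The window is 84 − 30 = 54 to 84 + 30 = 114 days after the last dose. A 16-week follow-up is 16 × 7 = 112 days. The amendment 7 rationale puts the median time to undetectable drug after weekly dosing at about 12 weeks (84 days). By the meaning of a median, about half of such patients would be undetectable at the nominal visit. No corresponding figure is given for 2-weekly dosing. With undetectable values set to zero, the row mean straddles the detection point.

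**3. Treatment gaps (SAP 2.3).** First gap: 113/2678 = 4.2% of enrolled patients. Second gap: 272/2678 = 10.2%. If the groups do not overlap, at most 385/2678 = 14.4%. The first gap follows the 3-year treatment period, after which no sample is scheduled until week 260, so it touches few scheduled troughs. The second could affect a patient who resumed shortly before week 48, 100 or 124.

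**4. Illustrative size.** Let r be the 2-weekly/weekly trough ratio and p the share of samples on 2-weekly dosing. Neither is in the documents; r = 0.3 to 0.7 is an assumption.

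Pooled mean relative to weekly = (1 − p) + p·r. Dividing this by r gives it relative to 2-weekly.

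| p | r = 0.3 | r = 0.5 | r = 0.7 |
|---|---|---|---|
| 0.10 | 0.93 | 0.95 | 0.97 |
| 0.25 | 0.825 | 0.875 | 0.925 |
| 0.50 | 0.65 | 0.75 | 0.85 |

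At p = 0.50 the pooled mean is 2.17, 1.50 and 1.21 times the 2-weekly mean.

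For within-subject spread, take a patient with k = 4 troughs, a fraction f = 1/4 of them on 2-weekly dosing, and an assumed true log-scale SD w = 0.3. With no regimen or visit term, the apparent SD is √(w² + k·f·(1 − f)·(ln r)²/(k − 1)) = √(0.09 + 0.25·(ln r)²). This gives 0.67, 0.46 and 0.35 for r = 0.3, 0.5 and 0.7. A visit term would absorb the change if every patient switched at the same visit.

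**The case against.** The strongest reply is that this is an under-specified outline and not a wrong analysis. Protocol 9.5.4 makes the model optional, names no terms and limits it to steady-state troughs. End-of-study and other off-drug samples would fall outside it once steady state is defined. SAP version 2.0 has no trough model. It was written for amendments 6 to 8, before 2-weekly dosing existed in the protocol. SAP section 7 leaves later analyses to an addendum, and protocol section 9 lets the SAP be revised for amendments. Main-study PK is not an endpoint, and protocol 9.5.5 examines individual profiles, where a dosing change can be seen.

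Most of this stands, and it limits the point. A reader might infer that the concentration outputs describe no regimen at all, that the SAP runs a pooled mixed model, or that the protocol has chosen a model by nominal visit without regimen. The documents support none of these. Weeks 48 and 100 are essentially one regimen; the sub-study has its own PK set and is all 300 mg every 2 weeks; and the protocol is silent on model terms. It would also be unfair to fault SAP version 2.0 for omitting a regimen that its governing amendments did not contain.

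Three things remain. The synopsis commits to the least-square-mean analysis that 9.5.4 makes optional. Protocol 9.5.4 is current text after amendment 9, yet it has no counterpart to the weekly and 2-weekly split in 9.5.2.3. And the descriptive rows, followed as written, pool across regimen and off-drug interval.

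**Conclusion.** The point holds for a limited set of outputs: the descriptive rows at week 124, week 260, early termination, end of study and, for 200 mg, the early visits before amendment 6; and any least-square means or within-subject variance pooled over them. End of study is the clearest case, because the mixed follow-up lengths and wide window come from the documents themselves. Weeks 48 and 100 are largely unaffected, apart from any sample taken soon after a second-gap resumption, and so is the sub-study.

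The size cannot be established. At an assumed trough ratio of 0.3 to 0.7, a 50:50 mix pulls the pooled mean to 0.65 to 0.85 of the weekly mean. At a 10% share on 2-weekly dosing it stays at 0.93 to 0.97. The ratio, the share and the within-subject SD of 0.3 are all assumptions. A reader might infer that the distortion is large, or that antibody conclusions are compromised. The documents do not show either. This is a modest, inexpensive improvement to a supportive analysis, worth making before the SAP is finalised.

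**What to change.** In protocol 9.5.4 and in the next version of SAP 5.9:

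- Present main-study concentrations by sampling time and by regimen in force at the sample (200 mg weekly, 300 mg weekly, 300 mg every 2 weeks).
- If the steady-state trough model is run, define steady state so that samples soon after a regimen change or a treatment gap are excluded. Include regimen as a fixed effect and report least-square means per regimen. Align the wording of 9.5.4 with the synopsis on whether the model will be run.
- Present end-of-study concentrations by last regimen and actual days since the last dose, not as one nominal row.

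The cost is wording, a few extra table columns and one model term; no new data are needed. Actual sample times are PK variables (SAP 4.7), and dose dates are in the dose administration listing (SAP 5.5). Some cells, such as 200 mg, will be small and may only merit a listing. SAP 10.9 notes that many home injections went unreported in the diary system, so days since last dose will be uncertain for some patients and should be flagged.

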#### 9.5.5. Analysis of Anti-Drug Antibody Data

The ADA variables described in Section 8.4 will be analyzed using descriptive statistics. Drug concentration data will be examined and the influence of ADAs on individual concentration-time profiles will be evaluated. Assessment of the impact of ADA on safety and efficacy may be provided.

#### 9.5.6. Analysis of the Sub-Study

Demographic and baseline characteristics will be summarized descriptively. Safety analyses will be conducted in descriptive fashion as described in Section 9.5.2.1 and Section 9.5.2.2. Efficacy analyses will be conducted in descriptive fashion as described in Section 9.5.3. Treatment compliance and treatment exposure will be analyzed in a similar fashion as described in Section 9.5.2.3 and Section 9.5.2.4.

Under Amendment 10, a primary analysis of the sub-study is planned once all patients who enter the sub-study complete 12 weeks of the new dupilumab drug product treatment period (sub-study week 12a visit or earlier for those patients who are withdrawn prematurely from the study).

**9.5.6.1. Statistical Hypothesis for the Sub-Study**

There is no statistical hypothesis for the sub-study.

**9.5.6.2. Justification of the Sub-Study Sample Size**

No formal sample size or power calculations were performed for the sub-study.

**9.5.6.3. Analysis Sets for the Sub-Study****Safety Analysis Set:**

The sub-study SAF includes all patients who receive any new dupilumab drug product in the sub-study. Efficacy, treatment compliance/administration, and all clinical safety variables will be analyzed using the SAF, as treated.

**Pharmacokinetic Analysis Sets:**

The sub-study PK population includes all treated patients who enter the sub-study (implemented under amendment 10), who receive any new dupilumab drug product, and who have a qualified result for drug concentration at any time during the sub-study period.

**Anti-Drug Antibody Analysis Set**

The sub-study ADA population includes all treated patients who receive any new dupilumab drug product and have at least 1 qualified result at any time during the sub-study period after the first dose of new dupilumab drug product. All ADA analysis will be conducted using this population.

